### 14.2.3.2 Time to event variables

#### 14.2.3.2.1 Progression-free survival

Usually in all Oncology studies, subjects are followed for tumor progression after discontinuation of study medication for reasons other than progression or death. If this is not used, e.g. in Phase I or II studies, this should be clearly stated in the protocol. Note that randomized trials (preferably blinded) are recommended where PFS is to be the primary endpoint.

**Progression-free survival (PFS)** is the time from date of randomization/start of treatment to the date of event defined as the first documented progression or death due to any cause. If a subject has not had an event, progression-free survival is censored at the date of last adequate tumor assessment.

PFS rate at x weeks is an additional measure used to quantify PFS endpoint. It is recommended that a Kaplan Meier estimate is used to assess this endpoint.

#### 14.2.3.2.2 Overall survival

All subjects should be followed until death or until subject has had adequate follow-up time as specified in the protocol whichever comes first. The follow-up data should contain the date the subject was last seen alive / last known date subject alive, the date of death and the reason of death (“Study indication” or “Other”).

**Overall survival (OS)** is defined as the time from date of randomization/start of treatment to date of death due to any cause. If a subject is not known to have died, survival will be censored at the date of last known date subject alive.

#### 14.2.3.2.3 Time to progression

Some studies might consider only death related to underlying cancer as an event which indicates progression. In this case the variable “Time to progression” might be used. TTP is defined as PFS except for death unrelated to underlying cancer.

**Time to progression (TTP)** is the time from date of randomization/start of treatment to the date of event defined as the first documented progression or death due to underlying cancer. If a subject has not had an event, time to progression is censored at the date of last adequate tumor assessment.

#### 14.2.3.2.4 Time to treatment failure

This endpoint is often appropriate in studies of advanced disease where early discontinuation is typically related to intolerance of the study drug. In some protocols, time to treatment failure may be considered as a sensitivity analysis for time to progression. The list of discontinuation reasons to be considered or not as treatment failure may be adapted according to the specificities of the study or the disease.

**Time to treatment failure (TTF)** is the time from date of randomization/start of treatment to the earliest of date of progression, date of death due to any cause, or date of

discontinuation due to reasons other than ‘Protocol violation’ or ‘Administrative problems’. The time to treatment failure for subjects who did not experience treatment failure will be censored at last adequate tumor assessment.

#### 14.2.3.2.5 Duration of response

The analysis of the following variables should be performed with much caution when restricted to responders since treatment bias could have been introduced. There have been reports where a treatment with a significantly higher response rate had a significantly shorter duration of response but where this probably primarily reflected selection bias which is explained as follows: It is postulated that there are two groups of subjects: a good risk group and a poor risk group. Good risk subjects tend to get into response readily (and relatively quickly) and tend to remain in response after they have a response. Poor risk subjects tend to be difficult to achieve a response, may have a longer time to respond, and tend to relapse quickly when they do respond. Potent agents induce a response in both good risk and poor risk subjects. Less potent agents induce a response mainly in good risk subjects only. This is described in more detail by (Morgan 1988).

It is recommended that an analysis of all subjects (both responders and non-responders) be performed whether or not a “responders only” descriptive analysis is presented. An analysis of responders should only be performed to provide descriptive statistics and even then interpreted with caution by evaluating the results in the context of the observed response rates. If an inferential comparison between treatments is required this should only be performed on all subjects (i.e. not restricting to “responders” only) using appropriate statistical methods such as the techniques described in Ellis, et al (Ellis et al 2008). It should also be stated in the protocol if duration of response is to be calculated in addition for unconfirmed response.

For summary statistics on “responders” only the following definitions are appropriate. (Specific definitions for an all-subject analysis of these endpoints are not appropriate since the status of subjects throughout the study is usually taken into account in the analysis).

**Duration of overall response (CR or PR):** For subjects with a CR or PR (which may have to be confirmed the start date is the date of first documented response (CR or PR) and the end date and censoring is defined the same as that for time to progression.

[figure not shown]
The following two durations might be calculated in addition for a large Phase III study in which a reasonable number of responders is seen.

**Duration of overall complete response (CR):** For subjects with a CR (which may have to be confirmed) the start date is the date of first documented CR and the end date and censoring is defined the same as that for time to progression.

**Duration of stable disease (CR/PR/SD):** For subjects with a CR or PR (which may have to be confirmed) or SD the start and end date as well as censoring is defined the same as that for time to progression.

#### 14.2.3.2.6 Time to response

**Time to overall response (CR or PR)** is the time between date of randomization/start of treatment until first documented response (CR or PR). The response may need to be confirmed depending on the type of study and its importance. Where the response needs to be confirmed then time to response is the time to the first CR or PR observed.

Although an analysis on the full population is preferred a descriptive analysis may be performed on the “responders” subset only, in which case the results should be interpreted with caution and in the context of the overall response rates, since the same kind of selection bias may be introduced as described for duration of response in [Section 14.2.3.2.5](#). It is recommended that an analysis of all subjects (both responders and non-responders) be performed whether or not a “responders only” descriptive analysis is presented. Where an inferential statistical comparison is required, then all subjects should definitely be included in the analysis to ensure the statistical test is valid. For analysis including all subjects, subjects who did not achieve a response (which may have to be a confirmed response) will be censored using one of the following options.

- at maximum follow-up (i.e. FSFV to LSLV used for the analysis) for subjects who had a PFS event (i.e. progressed or died due to any cause). In this case the PFS event is the worst possible outcome as it means the subject cannot subsequently respond. Since the statistical analysis usually makes use of the ranking of times to response it is sufficient to assign the worst possible censoring time which could be observed in the study which is equal to the maximum follow-up time (i.e. time from FSFV to LSLV)
- at last adequate tumor assessment date otherwise. In this case subjects have not yet progressed so they theoretically still have a chance of responding

**Time to overall complete response (CR)** is the time between dates of randomization/start of treatment until first documented CR. Similar analysis considerations including (if appropriate) censoring rules apply for this endpoint described for the time to overall response endpoint.

#### 14.2.3.2.7 Definition of start and end dates for time to event variables

##### **Assessment date**

For each assessment (i.e. evaluation number), the **assessment date** is calculated as the latest of all measurement dates (e.g. X-ray, CT-scan) if the overall lesion response at that assessment is CR/PR/SD/UNK. Otherwise - if overall lesion response is progression - the assessment date is calculated as the earliest date of all measurement dates at that evaluation number.

In the calculation of the assessment date for time to event variables, any unscheduled assessment should be treated similarly to other evaluations.

##### **Start dates**

[figure not shown]
For all “time to event” variables, other than duration of response, the randomization/ date of treatment start will be used as the start date.

For the calculation of duration of response the following start date should be used:

- Date of first documented response is the assessment date of the first overall lesion response of CR (for duration of overall complete response) or CR / PR (for duration of overall response) respectively, when this status is later confirmed.

##### **End dates**

The end dates which are used to calculate ‘time to event’ variables are defined as follows:

- Date of death (during treatment as recorded on the treatment completion page or during follow-up as recorded on the study evaluation completion page or the survival follow-up page).
- Date of progression is the first assessment date at which the overall lesion response was recorded as progressive disease.
- Date of last adequate tumor assessment is the date the last tumor assessment with overall lesion response of CR, PR or SD which was made before an event or a censoring reason occurred. In this case the last tumor evaluation date at that assessment is used. If no post-baseline assessments are available (before an event or a censoring reason occurred) the date of randomization/start of treatment is used.
- Date of next scheduled assessment is the date of the last adequate tumor assessment plus the protocol specified time interval for assessments. This date may be used if back-dating is considered when the event occurred beyond the acceptable time window for the next tumor assessment as per protocol.

**Example** (if protocol defined schedule of assessments is 3 months): tumor assessments at baseline - 3 months - 6 months - missing - missing - PD. Date of next scheduled assessment would then correspond to 9 months.

- Date of discontinuation is the date of the end of treatment visit.
- Date of last contact is defined as the last date the subject was known to be alive. This corresponds to the latest date for either the visit date, lab sample date or tumor assessment date. If available, the last known date subject alive from the survival follow-up page is used. If no survival follow-up is available, the date of discontinuation is used as last contact date.
- Date of secondary anti-cancer therapy is defined as the start date of any additional (secondary) anti-cancer therapy or surgery.

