#### **7.1.9 Survival follow-up**

Subjects will enter the survival follow-up period once they complete the safety follow-up and efficacy follow-up after study treatment discontinuation (whichever is longer). Subjects will then be contacted by telephone every 12 weeks ( $\pm 1$  week) until death, withdrawal of consent, lost to follow-up or end of study to follow-up on their survival status. Any new anti-cancer therapies that have been started since study treatment was discontinued will also be collected (radiotherapies, surgeries and medications, including regimen number, names of all medications received within each regimen and start/end dates for each medication) and any change or new anti-cancer therapy initiated since the last telephone contact date will be captured in the eCRF.

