## **Overall Survival**

Overall survival (OS) is defined as the time from date of randomization to date of death due to any cause. If a subject is not known to have died, then OS will be censored at the latest date the subject was known to be alive (on or before the cut-off date).

OS will be analyzed in the FAS population. The OS distribution will be estimated using the Kaplan-Meier method, and the Kaplan-Meier curves, medians and 95% confidence intervals of the medians will be presented for each treatment group.

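### Appendix 2's fallback for the last-contact date conflicts with the protocol's overall survival censoring rule, and would bias OS downward if it were programmed

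*Protocol*

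**What the plan says.** The protocol gives the OS censoring date in three places.

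- **Section 10.5.2, Overall Survival:** "OS will be censored at the latest date the subject was known to be alive", limited to dates on or before the cut-off.
- **Appendix 2, section 14.2.3.2.2:** "survival will be censored at the date of last known date subject alive".
- **Appendix 2, section 14.2.3.2.7, End dates, last-contact bullet.** It has four sentences. The first is the definition: "Date of last contact is defined as the last date the subject was known to be alive". The second names the sources: "This corresponds to the latest date for either the visit date, lab sample date or tumor assessment date". The third gives preference to the date on the survival follow-up page where there is one. The fourth is the fallback: "If no survival follow-up is available, the date of discontinuation is used as last contact date".

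The bullet just above the last-contact bullet fixes what the fallback means: "Date of discontinuation is the date of the end of treatment visit".

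Section 7.1.9 says when survival follow-up begins: "Subjects will enter the survival follow-up period once they complete the safety follow-up and efficacy follow-up after study treatment discontinuation (whichever is longer"). Sections 4.1.3 and 7.1.7 set safety follow-up at up to 150 days after the last dose, with contacts at 30, 60, 90, 120 and 150 days. Section 7.1.8 keeps subjects who stopped treatment without progression on the scan schedule until progression.

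**The concern.** A subject who stops treatment passes through safety follow-up, and possibly a long efficacy follow-up, before any survival record exists. At any cut-off some living subjects are in that gap. They have visits, calls or scans after EoT showing that they are alive. The fallback, taken at its word, discards those dates and returns the subject to the EoT visit. For a subject still on treatment it yields no date, because there has been no EoT visit.

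Deaths are handled differently. The End dates list takes the date of death whether it falls during treatment or follow-up, so a death in the same gap is counted at its true date. Dropping living subjects while keeping the deaths pushes the OS curve down. OS is reported for every arm.

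**Working it through.** **1. The rules side by side.** Take a subject who is alive at cut-off, off treatment, and in safety or efficacy follow-up.

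- Section 10.5.2: latest date known alive, hence the most recent contact.
- Section 14.2.3.2.2: last known date alive, hence the same.
- Last-contact bullet, first two sentences: latest visit, laboratory or tumor assessment date, hence the same apart from telephone calls.
- Last-contact bullet, last sentence: EoT visit.

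The last sentence cannot be applied together with the others for this subject.

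**2. Direction.** At a death time t the Kaplan-Meier hazard contribution is d/n, with d deaths and n subjects at risk. The fallback removes from the risk set the m living subjects whose EoT was before t but who were known alive at t. The contribution becomes d/(n − m), with d unchanged. Since m ≥ 0, the estimated hazard can only rise and the survival curve can only fall.

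**3. Size.** The protocol states no OS planning figure, so there is nothing to reproduce and the size rests on assumptions.

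Inputs from the protocol:
- 8 subjects per month (section 10.8.1, stated for the randomized section; used for illustration)
- 100 subjects for arm 1A (section 4.1.2), giving 100/8 = 12.5 months of accrual
- minimum follow-up of 9 months at the primary analysis and 15 months at end of study (section 4.3), and 20 weeks (about 4.6 months) as at an interim look
- 150 days of safety follow-up, taken as 5.0 months
- survival calls every 12 weeks (section 7.1.9)

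Assumptions: exponential OS with median 8, 12 or 18 months; exponential time to EoT with median 3 or 5 months; uniform accrual; 200,000 simulated subjects per scenario. The known-alive rule censors at the cut-off. The fallback censors at EoT if the subject is alive, off treatment and has no survival record. That record is taken to start either at day 150 after EoT or 12 weeks later, at the first survival call.

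12-month OS (%) at 9 months' minimum follow-up:

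| True median OS (months) | Median time to EoT (months) | Known-alive rule | Fallback, record from day 150 | Fallback, record from first call |
|---|---|---|---|---|
| 8 | 3 | 35.4 | 34.9 | 33.4 |
| 8 | 5 | 35.6 | 34.9 | 33.4 |
| 12 | 3 | 50.0 | 49.5 | 47.9 |
| 12 | 5 | 50.1 | 49.4 | 47.9 |
| 18 | 3 | 62.9 | 62.4 | 60.9 |
| 18 | 5 | 62.9 | 62.4 | 61.0 |

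- The known-alive rule recovers the true values (35.4, 50.0 and 63.0) within simulation error. The fallback loses 0.5 to 0.7 points (record from day 150) or 1.9 to 2.2 points (record from first call).
- For a true median of 12 months, the estimated median is 11.8 or 11.3 months instead of 12.0.
- Between 3% and 16% of subjects are affected. With the record starting at the first call, each loses 4.6 to 5.0 months on average.
- At 20 weeks' minimum follow-up, 12-month OS falls by 1.9 to 2.2 points (day 150) or 5.2 to 6.7 points (first call).
- At 15 months the two rules differ by at most 0.1 point.

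**4. Long efficacy follow-up.** The runs above do not model it. A separate run with median treatment of 4 months, true median OS of 12 months and 9 months' minimum follow-up gave 5.5% of subjects affected and a median of 11.8 months with nobody in long efficacy follow-up. With 10% to 20% of subjects there, 9% to 12% were affected and the median was 10.9 to 11.4 months. The 10% to 20% is assumed; the protocol gives no such figure.

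**The case against.** A reader might infer that the protocol adopts EoT censoring for OS, and that the reported curves will therefore be biased low. The documents do not support that. The two OS definitions contain no such fallback, and the last-contact bullet opens with the correct definition. Appendix 2 is a generic sponsor guideline (section 7.2.1), and section 14.2.4.1 leaves study-specific decisions to the protocol or the analysis plan. Section 10.5.2 is the study-specific text, and under it there is no bias. The fallback may have been meant only for subjects with no contact after EoT, for whom it does no harm. The statistical analysis plan, which was not available for this review, may settle the derivation.

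Three further inferences also go too far.

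- **Every affected subject loses at least 150 days.** A subject still in safety follow-up loses only the time since EoT, from near zero up to about 150 days.
- **The loss falls mainly on responders who stopped for toxicity.** Nothing here models response or the reason for stopping.
- **Early-look decisions would be distorted.** The formal rules are on confirmed response rate. Sections 4.2.1 and 4.2.2 say other available data are considered, but there is no OS criterion.

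These points limit the finding without removing it. Section 10.5.2 states the principle but not which records supply the date. The last-contact bullet is the only text that names the sources, and its last sentence points to the wrong one for subjects seen after EoT. Section 14.2.3.2.2 does not resolve this, because its term for the date is the one the bullet uses for the survival-page field.

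**Conclusion.** Wrong as written, low severity. The last sentence of the last-contact bullet contradicts the bullet's own definition and both OS censoring rules. If it were programmed, Kaplan-Meier OS would be biased downward, because survival follow-up starts only after safety and efficacy follow-up have ended. The direction follows from the rule itself.

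The size does not. It rests on exponential survival with medians of 8 to 18 months, assumed treatment durations and an assumed start of the survival record. On that basis it is about 0.5 to 2 percentage points on 12-month OS at the 9-month primary analysis. It would be larger if many subjects stayed in long efficacy follow-up, about 2 to 7 points at a 20-week look, and about nil at 15 months.

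OS is a secondary endpoint summarised descriptively for each treatment group, with no hypothesis test and no formal decision rule attached, so no primary conclusion of the trial is at risk.

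**What to change.** Delete the last sentence of the last-contact bullet in section 14.2.3.2.7, or replace it with:

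> If no survival follow-up is available, the latest visit, telephone contact, laboratory sample, tumor assessment or dosing date on or before the cut-off is used.

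Naming telephone contacts matters because the 60-, 90- and 120-day safety contacts may be calls. Section 10.5.2 already states the correct principle and needs no change. The cost is one sentence and one line of programming, using data already collected.

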#### 14.2.3.2.8 Handling of subjects with non-measurable disease only at baseline

It is possible that subjects with only non-measurable disease present at baseline are entered into the study, either because of a protocol violation or by design (e.g. in Phase III studies with PFS as the primary endpoint). In such cases the handling of the response data requires special consideration with respect to inclusion in any analysis of endpoints based on the overall response evaluations.

It is recommended that any subjects with only non-measurable disease at baseline should be included in the main (ITT) analysis of each of these endpoints.

Although the text of the definitions described in the previous sections primarily relates to subjects with measurable disease at baseline, subjects without measurable disease should also be incorporated in an appropriate manner. The overall response for subjects with non-measurable disease is derived slightly differently according to [Table 14-8](#).

**Table 14-8 Overall lesion response at each assessment: subjects with non-target disease only**

Non-target lesions	New Lesions	Overall lesion response
CR	No	CR
Non-CR/Non-PD 	No	Non-CR/non-PD
UNK	No	UNK
PD	Yes or No	PD

Non-target lesions	New Lesions	Overall lesion response
Any	Yes	PD

 As defined in Section 14.2.2.3.

In general, the **non-CR/non-PD response** for these subjects is considered equivalent to an SD response in endpoint determination. In summary tables for best overall response subjects with only non-measurable disease may be highlighted in an appropriate fashion e.g. in particular by displaying the specific numbers with the non-CR/non-PD category.

In considering how to incorporate data from these subjects into the analysis the importance to each endpoint of being able to identify a PR and/or to determine the occurrence and timing of progression needs to be taken into account.

**For ORR** it is recommended that the main (ITT) analysis includes data from subjects with only non-measurable disease at baseline, handling subjects with a best response of CR as “responders” with respect to ORR and all other subjects as “non-responders”.

**For PFS**, it is again recommended that the main ITT analyses on these endpoints include all subjects with only non-measurable disease at baseline, with possible sensitivity analyses which exclude these particular subjects. Endpoints such as PFS which are reliant on the determination and/or timing of progression can incorporate data from subjects with only non-measurable disease.

